January 16, 2022

Administration of follicle-stimulating hormone (FSH) and low dose human chorionic gonadotropin (hCG) for oocyte maturity while decreasing hCG exposure in In Vitro fertilization (IVF) cycles

NCT02310919

Study Protocol

Specific Aims

Primary Aim:

1) To determine if concomitant low dose hCG (1500 IU) and 450 IU FSH for oocyte maturation trigger is non-inferior to the standard hCG alone in total fertilization proportion (i.e. total competent proportion), according to the primary outcomes involving maturation and fertilization:

Total fertilization proportion (i.e. total competent proportion), defined as the number of fertilized oocytes (2PN) divided by the total number of oocytes retrieved, will be compared between the two treatment groups.

2) To further assess the outcomes of oocyte recovery and developmental competence of the mature oocytes the following will be compared between the two treatment groups:

- a) Oocyte recovery
- b) Oocyte maturity
- c) Fertilization rate
- d) Embryo quality
- e) Pregnancy rates

3) To compare serum and follicular post-trigger steroid hormones levels of estradiol, progesterone, hCG, FSH LH, and vascular endothelial growth factor (VEGF) between the two treatment groups at different times points:

- a) 12 hours after trigger (T+1), at oocyte retrieval (T+2), and 5 days after trigger (T+5) to assess serum levels of, as appropriate, based on the study visit day.
- b) Follicular fluid from the first aspirate of a dominant follicle on each ovary at retrieval

Secondary Aim: To determine if symptoms of OHSS are decreased with low dose hCG (1500 IU) and 450 IU FSH compared to standard hCG dose alone.

Compare symptoms related to OHSS using the following outcomes:

- 1) The change in bloating scores prior to trigger and after trigger
- 2) The change in abdominal circumference prior to trigger and after trigger
- 3) The change in body weight prior to trigger and after trigger

Experimental Design and Methods:

Study population:

The target population includes female patients undergoing IVF. All eligible female patients will be asked to join the study. Patients receiving any type of stimulation protocol for IVF will be offered participation in the study. Study participants will be recruited from the Reproductive Endocrinology Clinic at University of California at San Francisco Center for Reproductive Health.

Inclusion/Exclusion Criteria:

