Inclusions: Only patients undergoing IVF will be offered participation in the study.

Exclusions:

- Age >41 years old
- Antral Follicle Count (AFC; 2-10 mm) < 8
- Body Mass Index > 30 kg/m²
- History of ≥ 2 prior canceled IVF cycles secondary to poor response
- Diagnosis of cancer
- Any significant concurrent disease, illness, or psychiatric disorder that would compromise patient safety or compliance, interfere with consent, study participation, followup, or interpretation of study results
- Undergoing embryo co-culture
- Use of any of the following medications: Growth Hormone, Sildenafil, or Aspirin (except if being used for hypercoagulable state)
- Severe male factor infertility diagnosis. Male factor infertility diagnosis should be cleared for eligibility by the PI based on previous patient history of fertilization outcomes and/or expected fertilization outcomes of the cause of male factor infertility based on known scientific data.
- Ovulation trigger less than or greater than 36 hours to oocyte retrieval
- Serum estradiol level >5,000 pg/ml on the day of expected ovulation trigger

Recruitment Plan: The physician will identify patients eligible for the study at the consultation visit. A research coordinator will follow up and meet with eligible participants at the saline sonography visit or the patients next clinical visit prior to start of IVF treatment. Informed consent will be performed by the research coordinator.

Design: Double –Blinded Randomized trial

Randomization:

The patients will be randomized on the day of ovulation trigger for assignment to receive either standard dose of hCG (5,000 IU or 10,000 IU) alone or low dose hCG (1,500 IU) + FSH (450 IU) for oocyte maturation trigger by the research coordinator. All participants will be assigned a unique subject ID, and only the research coordinator and unblinded study physician will be aware of what treatment arm each patient is in. All other physicians, nurses, embryologists, clinic staff, and patients will be blinded.

Blinding process for the medication administration:

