The hCG and FSH trigger shots for each patient will be prepared by the unblinded study physician the same day the patient will administer the medications. Each medication will be reconstituted in their own separate syringe so the patient will be presented with two syringes for administration that will be labeled with only “hCG” and “other”. The hCG sterile powder will be reconstituted with bacteriostatic water, and the designated dose suspended in a total volume of 1 ml in a syringe by the unblinded study physician or nurse. It will only be labeled with “hCG” and excluding the dose. The FSH sterile powder will also be reconstituted with bacteriostatic water and suspended in a total volume of 1 ml in a syringe, then labeled “other”.

The patients that were not randomized to receive the FSH co-trigger will receive a similar syringe with only 1 ml of bacteriostatic water and no FSH, also labeled "other". Immediately after reconstitution and suspension, the trigger medication will be given to the patient. Each designated syringe will be placed in an insulated cooler travel container for the patient to take to administer that day based on assigned trigger time. Since the unblinded study physician will be preparing the trigger shots for each patient they will be aware of what treatment arm each patient is in.

Treatment Plan:

The subjects will undergo ovarian stimulation with IVF protocol stimulation treatment chosen by their primary doctor. Baseline antral follicle count (AFC) will be recorded.

Standard of care guidelines for ovarian stimulation to be used as a reference (not part of the experimental protocol):

Type of gonadotropins: FSH, (i.e. Gonal-F) + hMG, (ie. Menopur)

Starting dose of gonadotropins is 150-450 IU per day of FSH and hMG, which are standard starting doses in our clinical practice. Initial dose will be determined by the patient's primary doctor based on AFC and body weight. As per standard practice, the minimal dose for the desired response will be used. The primary doctor will manage the entire ovarian stimulation based on their clinical knowledge, expertise, and standard of care practices.

Standard Guidelines:

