Analyses will be performed based on intention-to-treat (ITT). Using the standard trigger as reference, the relative risk and associated 95% confidence interval (CI) for the probability of laboratory outcomes was calculated using log-binomial regression models. Generalized estimating equations (GEE) with an exchangeable correlation structure was applied to account for clustered data (i.e. oocytes and embryos originating from the same patient). Continuous laboratory outcomes were compared using generalized linear modeling with log link function. For pregnancy outcomes, relative risk and 95% CI were calculated to estimate effect size. Hormone concentrations were compared using Wilcoxon rank sum test. For the non-inferiority hypothesis testing of the primary outcome, a one-sided 95% CI was constructed for the relative risk. The alternative trigger will be considered non-inferior to the standard trigger if the lower bound of the one-sided CI of the relative risk is not less than 0.8 (i.e. risk reduction limit of 20%). For secondary outcomes, the statistical significance was based on a two-sided alpha of 0.05. Data were analyzed using SPSS version 28.0.1.0 (Statistical Package for Social Sciences; Chicago, IL).

For the secondary aim evaluating OHSS related symptoms, the abdominal circumference, body weight, and bloating score will be analyzed using t-tests to determine if the change is significantly different between the trigger groups. For these secondary aim outcomes, we do not expect to have sufficient numbers of events to conduct a formal analysis.

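### Oocyte recovery (Aim 2a) has no stated metric; if it is the number of oocytes retrieved, its model names no covariate and forgoes the precision that the recorded baseline AFC could give

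*Combined protocol and SAP*

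**What the plan says.** Under Specific Aims, the second part of the Primary Aim is "To further assess the outcomes of oocyte recovery and developmental competence of the mature oocytes", and the first item in its list is given only as "a) Oocyte recovery". No unit, denominator or definition follows, there or elsewhere.

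On timing, the Randomization section says "The patients will be randomized on the day of ovulation trigger". Stimulation comes before that. Under Study population, "Patients receiving any type of stimulation protocol for IVF will be offered participation in the study"; under Treatment Plan and Standard Guidelines, the primary doctor chooses and manages the stimulation, which runs until trigger.

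On the baseline measure, the Treatment Plan says "Baseline antral follicle count (AFC) will be recorded". The documents use AFC for eligibility (a count below 8 excludes; no upper limit is set) and for choosing the starting dose.

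On analysis, the Statistical analysis section says "Continuous laboratory outcomes were compared using generalized linear modeling with log link function". It names no covariate for that model. A separate sentence assigns outcomes that are probabilities to log-binomial regression with GEE, with the standard trigger as reference. Neither that section nor the Randomization section mentions stratification or baseline adjustment.

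**The concern.** By the time a woman is randomised, the number of follicles she has depends on her ovarian reserve and on the stimulation her doctor chose. The trigger can act only on how many of those follicles yield an oocyte. If the outcome is a raw count, the variation between women in cohort size goes into the error term unless the model contains something that explains it. AFC is available before randomisation and is a natural candidate.

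This outcome matters for reading the primary result. The primary outcome divides fertilised (2PN) oocytes by oocytes retrieved. If one trigger yielded fewer oocytes, numerator and denominator could shrink together and leave the ratio unchanged. Oocyte recovery is the listed outcome that would show such a loss directly. The trial is sized only for the primary ratio, so a non-significant recovery result could be taken as reassurance when the comparison is simply noisy.

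**Working it through.** **The plan's own figure.** The only sample size given is for the primary outcome. Inputs from the sample size section: proportion 0.5, non-inferiority difference 0.1, one-sided alpha 0.05, power 0.8, cluster size 15, intra-cluster correlation 0.1.

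- Oocytes per arm, ignoring clustering: (1.645 + 0.842)² × 2 × 0.5 × 0.5 / 0.1², which is 310 when rounded up.
- Design effect: 1 + (15 − 1) × 0.1 = 2.4.
- Women per arm: 310 × 2.4 / 15 = 49.6, so 50.

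The stated 50 per arm reproduces, and nothing below disturbs it. No corresponding calculation is given for oocyte recovery.

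**Inputs for oocyte recovery, read as number retrieved**

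- From the documents: 50 women per arm; two-sided alpha 0.05 for secondary outcomes; a mean of 15 oocytes (used in the simulation below).
- Assumed: between-woman coefficient of variation (CV) of the oocyte count, 0.45 to 0.55; correlation r of AFC with oocyte count, 0.3 to 0.7; a 20% loss (ratio 0.8) as an illustrative effect.

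**Formulas**

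- SE of the log ratio of means = CV × √(2/50) × √(1 − r²), with r = 0 for the unadjusted comparison.
- Power = Φ(−ln 0.8 / SE − 1.96), where −ln 0.8 = 0.223.
- Equivalent unadjusted number per arm = 50 / (1 − r²).

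| r | SE, CV 0.45 | Power | SE, CV 0.55 | Power | Fall in SE | Equivalent n per arm |
|---|---|---|---|---|---|---|
| unadjusted | 0.090 | 0.70 | 0.110 | 0.53 | – | 50 |
| 0.3 | 0.086 | 0.74 | 0.105 | 0.57 | 5% | 55 |
| 0.5 | 0.078 | 0.82 | 0.095 | 0.65 | 13% | 67 |
| 0.7 | 0.064 | 0.93 | 0.079 | 0.81 | 29% | 98 |

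For example, at CV 0.45 and r = 0.3: SE = 0.45 × 0.2 × √0.91 = 0.086; 0.223 / 0.086 − 1.96 = 0.64; Φ(0.64) = 0.74.

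**Check by simulation.** A log-link model was fitted with and without log AFC to simulated counts (mean 15, 50 per arm, AFC at least 8). The documents name no distribution for this model; a Poisson model with robust standard errors was assumed. At correlations of about 0.34, 0.54 and 0.69, the ratio of adjusted to unadjusted variance was 0.91, 0.70 and 0.55. The square roots are 0.95, 0.84 and 0.74, so the standard error fell by about 5%, 16% and 26%, in line with the table. Both estimators were unbiased.

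**The case against.** The strongest objection is that the outcome has been assumed. Oocyte recovery could mean oocytes per follicle aspirated; the protocol does have all visible follicles aspirated. It would then fall under the log-binomial GEE model, the cohort size would already be in the denominator, and AFC would add less. This stands, and it is why the point is conditional and why the missing definition comes first in the fix.

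Second, AFC is measured before stimulation and cannot capture differences in protocol or dose. A follicle count at trigger would lie closer to the argument. That also stands, but the documents do not list such a count among the recorded data, whereas they do list AFC.

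Third, the correlation may be modest. The starting dose is set partly from AFC and then adjusted on response, low AFC is excluded, and so is very high estradiol (fewer than 5% of subjects expected). All of this could weaken the link, so the range has to reach down to r = 0.3, where the gain is small.

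A reader might infer more than the documents support:

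- **That the unadjusted comparison is biased, or that chance imbalance in AFC invalidates it.** It does not. Randomisation follows stimulation, and chance imbalance is part of the sampling error that the confidence interval already reflects.
- **That the plan rules out adjustment.** It is silent; the sentence on the log-link model states no model terms at all.
- **That the trial's 20% margin applies to recovery.** That margin belongs to the primary proportion. No margin, effect size or power is set for recovery, and modest power for an outcome the trial was not sized on is not in itself an error.
- **That AFC goes unused.** It serves eligibility and dosing; only the analysis omits it.

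**Conclusion.** The point holds as one of definition and precision. Oocyte recovery lacks a metric. If it is the number retrieved, the planned comparison is valid but less precise than the trial's own data allow. The gain from AFC ranges from slight (SE down about 5%, power 0.70 to 0.74 or 0.53 to 0.57) to substantial (SE down 29%, power up to 0.93 or 0.81). The documents cannot fix where in that range the trial lies, because both the CV and the correlation are assumptions. The primary non-inferiority test and the sample size of 50 per arm are unaffected. Priority is minor to moderate: a supporting outcome, but the one that shows a loss the primary ratio could miss.

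**What to change.** In the Statistical analysis section:

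1. State that oocyte recovery (Aim 2a) is the number of oocytes retrieved per woman.
2. State that its log-link model contains trigger arm and log baseline AFC.
3. Report the AFC-adjusted ratio of means with its 95% CI as the main oocyte-recovery result, with the unadjusted ratio beside it.

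If the sponsor intends a per-follicle measure instead, the section should say so, name the denominator, and place the outcome under the log-binomial GEE model.

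The cost is one or two sentences. AFC is already recorded and precedes assignment, so the trigger cannot affect it; no new data, visits or participants are needed. Parts of the section are written in the past tense. If outcome data have already been analysed, the adjusted result should be labelled as not pre-specified.

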Gonadotropin medications will be started as designated by the patient's primary doctor and baseline ultrasound is performed. Ultrasounds will be performed and serum estradiol (E2) will be checked as determined by the patient's primary doctor. Gonadotropin dose will be adjusted based on ultrasound findings and serum E2 level as needed to be determined by the patient's primary doctor. Gonadotropin injections will be continued until ovulation trigger.

The day of administration of ovulation trigger will be determined by the patient's primary doctor.

Guidelines for the experimental protocol:

Study participants will receive a syringe on the day of ovulation trigger containing either the standard dose of hCG or low dose hCG + FSH according to the randomization. The subjects will be triggered with the following:

- a) Standard dose of hCG (10,000 IU or 5,000 IU) or
- b) Low dose of hCG 1,500 IU SQ + FSH 450 IU SQ

For the control arm, the standard hCG dose will be given based on the E2 level on the day of ovulation trigger. If the E2 level is less than 3,500 pg/ml, then the trigger will be 10,000 IU of hCG. If the E2 level is more than 3,500 pg/ml but less than 5,000 pg/ml, then the trigger will be 5,000 IU.

On the day of ovulation trigger, the subject's body weight and abdominal circumference will be measured. The subject will also complete a questionnaire regarding her current symptoms. In

addition to the standard of care estrogen lab, residual blood from that draw will be retained by the study for an additional lab to assess additional hormone levels. Subjects will return 12 hours after trigger (T+1), at oocyte retrieval (T+2), and 5 days after trigger (T+5) to assess serum levels of estradiol, progesterone, hCG, FSH, LH, and vascular endothelial growth factor (VEGF), as appropriate, based on the study visit day.

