The oocyte retrieval will be performed 36 hours after the ovulation trigger. All egg retrievals will be performed using transvaginal ultrasound and the associated needle guide in the standard fashion. On the day of the oocyte retrieval, the patient will have a blood draw to assess serum hormone levels. When possible, efforts will be made to use pre-existing venipuncture, such as an intravenous line, to minimize needle sticks. In these instances, approximately 3-5 mL of blood will be drawn and discarded as waste to clear the line of possible heparin and/or saline flush, and have been factored into the total blood draw volumes required by the study.

Both the physician performing the oocyte retrieval and the laboratory personnel will be blinded to the study. All visible follicles will be aspirated. The first follicle from each ovary on every patient will be aspirated and the system (needle and tubing) will be flushed into a separate tube prior to aspirating the remaining follicles. The follicular fluid from the first aspirate from each ovary will be collected to assess follicular hormone levels. Oocyte stripping will be performed under the standard protocol. The status of oocyte maturation at the time of stripping (approximately 38-40 hours after hCG administration) and at the end of the ICSI procedure (approximately 40-42 hours after hCG administration) will be recorded. Fertilization will be assessed 16-19 hours after insemination. The embryos will be transferred to growth media and cultured with standard protocols.

Subjects will return five days after ovulation trigger for blood draw to assess serum hormone levels. The subject's body weight and abdominal circumference will be measured. The subject will complete a questionnaire regarding her current symptoms and bloating score.

Interventions to prevent OHSS in high risk patients:

Any patients in either arm with an E2 serum level >5,000 pg/ml on the day of expected trigger administration will be excluded from the study. These patients will be individually assessed by their primary physician. Their primary physician will decide the safest trigger option based on the patient's risk of OHSS. From our own clinical experience, we expect that <5% of subjects will have an E2 serum level of >5,000 pg/ml and be excluded.

Interventions to avoid ovulation trigger failure:

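### Post-trigger serum estradiol is compared without the trigger-day estradiol value that the protocol already requires, which gives up precision on a supportive outcome.

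*Combined protocol and SAP*

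**What the plan says.** Aim 3 compares serum and follicular hormone levels between the arms. The statistical analysis section covers all of them in one sentence: "Hormone concentrations were compared using Wilcoxon rank sum test". It names no covariate. Secondary outcomes are judged at a two-sided 5% level.

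Trigger-day serum estradiol has two roles before treatment:

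- Eligibility. The exclusion list includes "Serum estradiol level >5,000 pg/ml on the day of expected ovulation trigger".
- Dosing. Under the guidelines for the experimental protocol, for controls "the standard hCG dose will be given based on the E2 level on the day of ovulation trigger".

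On timing, the randomization section says "The patients will be randomized on the day of ovulation trigger". On follow-up, the guidelines say "Subjects will return 12 hours after trigger (T+1), at oocyte retrieval (T+2), and 5 days after trigger (T+5) to assess serum levels of estradiol", and go on to list the other analytes, with the proviso that measurement depends on the visit day. For other hormones at trigger, "residual blood from that draw will be retained by the study for an additional lab to assess additional hormone levels"; which ones will be assayed is not stated.

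**The concern.** The trigger-day estradiol value has to be known before the trigger can be chosen, so it precedes the randomized treatment and cannot be affected by it. It is the same analyte as the outcome, taken from the same participant, and it is already on record. A covariate of that kind is normally the first candidate for adjustment, yet it appears in no analysis.

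What is at stake is precision. If later estradiol depends on its trigger-day level, an unadjusted comparison leaves that between-patient variation in the error term. A real difference between the triggers is then more likely to be missed, although no further blood or participants would be needed to do better.

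**Working it through.** **Sample size.** The documents give no power figure for hormones, so the check uses the planned arm size. That figure reproduces:

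- Oocytes per arm: 2 × 0.5 × 0.5 × (1.645 + 0.842)² / 0.1² ≈ 309.1, or 310 in whole oocytes.
- Design effect: 1 + (15 − 1) × 0.1 = 2.4.
- Participants per arm: 310 × 2.4 / 15 = 49.6, so 50, as stated.

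**Inputs from the documents.** 50 per arm; two-sided 5%; trigger-day values above 5,000 pg/ml excluded, with the expectation that "we expect that <5% of subjects will have an E2 serum level of >5,000 pg/ml and be excluded". The simulation cuts off the top 5% of trigger-day values to represent this.

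**Assumed inputs.** A treatment difference of 0.5 SD on the log scale, and a correlation between trigger-day and later log estradiol of 0, 0.3, 0.5 or 0.7 before the cut-off. Neither is in the documents. The cut-off lowers 0.3 / 0.5 / 0.7 to about 0.27 / 0.46 / 0.66.

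**Hand check of the mechanism (normal residuals, no cut-off).** Adjustment multiplies the error variance by 1 − r²: 0.91, 0.75 and 0.51 at r = 0.3, 0.5 and 0.7. The unadjusted standardized effect is 0.5 × √(50/2) = 2.5. Adjusted power is roughly Φ(2.5/√(1 − r²) − 1.96):

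- r = 0.3: Φ(2.62 − 1.96) ≈ 0.75
- r = 0.5: Φ(2.89 − 1.96) ≈ 0.82
- r = 0.7: Φ(3.50 − 1.96) ≈ 0.94

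Simulated log-scale ANCOVA gives 0.73, 0.81 and 0.93, so the approximation runs about 0.01 to 0.02 high.

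**Simulated power with the top 5% cut off.** Quade's method ranks the outcome and the covariate, regresses one set of ranks on the other, and compares the residuals between arms.

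| Assumed correlation | Rank-sum | Quade's rank ANCOVA | Difference |
|---|---|---|---|
| 0 | 0.67 | 0.67 | 0.00 |
| 0.3 | 0.69 | 0.71 | 0.02 |
| 0.5 | 0.69 | 0.78 | 0.09 |
| 0.7 | 0.71 | 0.91 | 0.20 |

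Separate runs agree to within about 0.01. With no true difference, both tests reject about 5% of the time.

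**Heavy-tailed case (t residuals with 3 df on the log scale, assumed).** This decides which adjusted method should lead.

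| Assumed correlation | Rank-sum | Log-scale ANCOVA | Quade |
|---|---|---|---|
| 0.3 | 0.89 | 0.78 | 0.92 |
| 0.5 | 0.85 | 0.84 | 0.94 |
| 0.7 | 0.80 | 0.93 | 0.98 |

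At zero correlation the log-scale ANCOVA falls to 0.74 against 0.91 for the rank-sum test. Quade's method keeps the robustness of ranks and adds the covariate. In the cases run it was never materially worse than the planned test.

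**The case against.** The strongest objection is that nothing here is an error. An unadjusted rank test is valid in a randomized comparison, and it is a reasonable choice for skewed concentrations. That stands: the point is one of efficiency. A reader might infer that the planned estradiol comparison is biased or has the wrong error rate. It does not; its type I error is about 5%.

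The gain is also unproven. The correlation is unknown and need not be the same at the three visits. All visible follicles are aspirated at retrieval, so estradiol 5 days after trigger may track the trigger-day value poorly. The trigger-day result is a same-day clinical measurement, while study serum is frozen and batched, which could weaken the correlation further. All of this stands, and it is why the zero-correlation row is shown. In that row Quade's method costs almost nothing (0.670 against 0.673).

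A replacement could do harm. That is true of log-scale ANCOVA used as the main test, as the heavy-tailed figures show, so it should not lead.

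The control dose depends on the covariate. This was examined for log-scale ANCOVA with a shift of −0.3 or −0.5 SD in an assumed 20% of controls above 3,500 pg/ml. With an average effect of zero, type I error stayed at 0.049 to 0.052.

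A stronger reading is tempting for the follicular samples. Aim 3 collects "Follicular fluid from the first aspirate of a dominant follicle on each ovary at retrieval", so a participant can contribute two values, and the stated clustering correction covers only oocytes and embryos. A reader might infer that the follicular tests reject too often. That would follow only if both ovaries were entered as separate observations and their values were positively correlated; at an assumed correlation of 0.5, a nominal 5% would become about 11%. The documents state neither condition, and one value per participant is not excluded. This is a detail to write down, not a demonstrated error.

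**Conclusion.** The point holds as a minor matter of precision, confined to serum estradiol. The plan requires a pre-treatment value of the outcome for eligibility and dosing but does not use it in the comparison. The cost is nothing at zero correlation, about 0.02 in power at 0.3, 0.09 at 0.5 and 0.20 at 0.7. These figures rest on 50 per arm, an assumed 0.5 SD log-scale effect, normal residuals and a 5% cut-off.

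The point does not extend to the other hormones unless they are assayed in the retained trigger-day blood, because only estradiol is assured at that time. It concerns a supportive outcome and leaves the primary non-inferiority conclusion untouched.

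**What to change.** Add to the statistical analysis section:

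> Post-trigger serum estradiol at each time point will be compared by Quade's rank ANCOVA adjusted for trigger-day serum estradiol; the unadjusted Wilcoxon rank-sum test is the sensitivity analysis. A log-scale ANCOVA adjusted for the log trigger-day value will supply the ratio of geometric means with 95% CI.

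Limit this to estradiol unless other trigger-day hormones are assayed. The section is written largely in the past tense. If the hormone analysis has already been run, keep the rank-sum result as the planned one and report the adjusted result as a labelled supplementary analysis.

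As a side clarification, state that follicular fluid contributes one value per participant to the rank-sum test: the mean of the log values from the two ovaries, or the single value if only one is available. If that was already intended, nothing changes.

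The cost is a few sentences and a little more analysis work. No new samples or participants are needed. Quade's method gives no effect estimate on the concentration scale, which is why the log-scale model is kept for the ratio.
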